### 3. STUDY PROCEDURES

After screening for HIV-negative patients ages 18-25 waiting to be seen by providers at Project Stay, informed consent will be given about the study. If the patient decides to participate in the study and agrees to the informed consent, the initial survey will be distributed either in hard-copy form or on an iPad (using a computer-assisted self-interview assessment) to obtain the data. Following the survey, the counselor will see whether or the patient is MSM, and perform stratified randomization based off this demographic. A third-party statistician will provide assignments in premade envelopes assigning participants based off blocked and stratified randomization to each arm of the study, which will not be opened until the participants has completed the survey. If the participant is assigned the control arm,

s/he will receive a pamphlet on the recent PrEP studies and asked to read over the information prior to seeing their provider. If the participant is assigned the interventional arm, the counselor will provide a one-on-one session on the recent PrEP results and answer any questions they might have, in addition to receiving the aforementioned pamphlet. All participants will then be asked to bring a sealed envelope to the provider, which will have three questions that the provider will fill out after their encounter with the patient:

1. Did the patient ask you about PrEP?
2. Did you bring up the subject of PrEP with the patient?
3. If yes to either, approximately how much time did you spend talking to the patient about PrEP?
4. Did the patient ask for a prescription for PrEP?

One week following the initial survey, participants will be contacted via e-mail about completing the final part of the study, which will include some of the same questions regarding knowledge, attitudes, and willing to use PrEP, as well as acceptability of other HIV prevention methods. This survey will be given using Survey Gizmo, a secure online survey provider service. Reminder e-mails will be sent up to 3 times, with a phone call follow up if the survey has not yet been completed. Participants will received a \$5 gift certificate to either Starbucks or McDonalds for completing the first portion of the study, and another \$5 gift certificate for completing the second/final part of the study.

Finally, we will look up patient's medical records to determine if prescriptions for PrEP were prescribed and whether or not they were filled at 0, 6, and 12 months.

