Secondary Objective #2: To determine specific concerns or barriers (e.g., concerns about potential side effects, concerns that I would increase risk taking behavior, don't feel that I am at risk for HIV, don't like taking pills, don't think the pill will protect me from getting HIV infected, concerns that if HIV medications are used now, they won't work in the future if I became HIV+, concerns that others might think I am HIV positive, concerns this would limit the availability of HIV medications for people infected with HIV, already using a strategy for prevention that is effective, concerned it is too expensive) that would prevent high-risk adolescents and young adults to use oral PrEP, and how this may be influenced by different modes of education.

Secondary Objective #3: To assess the acceptability of various methods of HIV prevention, including variations in the timing and way of administering PrEP (i.e. via IM, via microbicides, or intermittent dosing).

Statistical analysis of the questionnaire survey data will be performed using SAS software. Frequencies of responses to survey questions will be described. Chi square and Fisher's exact tests will be computed to compare pamphlet-educated participants' survey responses and PrEP prescriptions to the responses and prescriptions of participants educated by one-on-one counseling. Variables with p-value < 0.05 will be considered significant and will be included in multivariate logistic regression model. Forward selection will be used in the logistic regression model to evaluate variables independently associated with willingness to use PrEP. The outcome variables, whether or not they would use PrEP and bring the issue up with their provider, will be evaluated using a proportion and compared between groups; PrEP prescriptions written and filled at 0, 6, and 12 months will also be evaluated, proportion will be computed and then compared between groups.

The primary endpoint is the difference between the proportion of participants who asked their providers about PrEP in the intervention group versus control group. Because of the limited ability to survey 100 participants (50 in each group), we will use this fixed number of subjects in our power analysis to determine the smallest difference for which the available number of subjects will lead to statistical significance.

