A study in Boston found that 74% of MSM were interested in using PrEP after being educated in-person about its potential (12). Based off this information, one can assume that the proportion of those willing to use PrEP will be approximately 74% for the group with one-on-one counseling (+ pamphlet) on the recent PrEP results, and could lead to a corresponding 74% who will ask their providers about it. Using backward power calculation using our predetermined sample size of 50 in each group, with  $\alpha = .05$  and power = .80, we would find a difference between the two groups if the proportion of those who ask their provider about PrEP in the control group is < .46 (or > .96). Thus, the smallest difference for which our study will find a statistical difference between each group is .28.

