#### 10. PRIVACY PROTECTIONS

Only those conducting the study will have access to participants' information. Furthermore, participants may choose to not answer any question in the questionnaire if it makes them feel uncomfortable or skip a question for any reason.

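### The survey comparison of the arms after education rests on one remote survey and an unadjusted test that uses neither the baseline answers nor the MSM stratum

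*Protocol*

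**What the plan says.** Protocol section 2 (Study Design and Statistical Procedures) and section 3 (Study Procedures) have everyone complete an initial survey in the clinic. The assignment envelope, stratified by MSM status, stays closed until that survey is done. The only later measurement of knowledge, attitudes and willingness is a web survey e-mailed one week afterwards, with a further $5 gift certificate for completing it. On non-completion section 3 says: "Reminder e-mails will be sent up to 3 times, with a phone call follow up if the survey has not yet been completed". Section 10 (Privacy Protections) adds that "participants may choose to not answer any question in the questionnaire".

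The arm comparison is in section 2: "Chi square and Fisher's exact tests will be computed to compare pamphlet-educated participants' survey responses", and the responses of the counselled group. Willingness to use PrEP is among the outcome variables to be compared between groups, and Secondary Objective #2 asks how mode of education influences barriers. The only regression described selects variables by significance, so nothing ensures that the baseline answer or the stratum enters it.

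The primary outcome has a different source: "The primary endpoint is the difference between the proportion of participants who asked their providers about PrEP". It is recorded on the provider's form at the visit. Prescriptions come from medical records.

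**The concern.** A chi-square or Fisher test on a two-by-two table has no cell for a participant who did not answer, and no place for a baseline answer or a stratum. Applied as named to the one-week survey, it compares those who replied.

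The design makes unequal response plausible. One arm has had a personal session with the study counselor; the other has had a pamphlet. If counselling makes interested participants more likely to reply, or uninterested ones less likely, the responders in the two arms differ even when counselling changed nobody's willingness. At stake are the between-arm findings on willingness, knowledge and barriers.

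Leaving out the stratum is the lesser matter: it gives up precision but does not create the false difference.

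**Working it through.** **1. The plan's own figure, used as a yardstick.** Section 2 starts from 50 per arm ("Using backward power calculation using our predetermined sample size of 50 in each group"), two-sided alpha .05 (sidedness assumed), power .80 and a counselled proportion of .74. With the pooled formula,

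power = Φ{(d − 1.96·√(2p̄(1−p̄)/n)) / √((p1(1−p1)+p2(1−p2))/n)}.

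For .74 v .46, p̄ = .60 and n = 50: (.28 − 1.96 × .0980)/.0939 = .937, so power is .826. Power of .80 is reached at a control value of .469, a difference of .271. The stated .28 is slightly conservative. It is a figure for asking the provider; the plan gives none for the survey.

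**2. Assumptions.** The documents give no response rate, so every rate below is assumed. True willingness is 60% in both arms (no effect). In an arm where a fraction rw of the willing and ru of the unwilling reply, the observed proportion is .6rw/(.6rw + .4ru) and the response rate is .6rw + .4ru.

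**3. Observed proportions.**
- Same dependence in both arms (80% of willing, 60% of unwilling): .48/(.48 + .24) = 66.7% in each arm. The difference is 0, although both levels are 6.7 points too high.
- Counselled 80%/60%, controls 72% regardless: 66.7% v 60%, a false difference of 6.7 points, with 36 responders per arm.
- Counselled 80%/50%, controls 72% regardless: .48/(.48 + .20) = 70.6% v 60%, a false difference of 10.6 points, with 34 v 36 responders.

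**4. False-positive rates at nominal 5%.** With s0 the pooled and s1 the unpooled standard error, the normal approximation is Φ((d − 1.96·s0)/s1) + Φ((−d − 1.96·s0)/s1). The exact rates sum binomial probabilities over all tables that reject, with responder numbers held at their expected values.

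| Counselled response, willing/unwilling | d | s0, s1 | Normal approx. | Exact Pearson | Exact Fisher |
|---|---|---|---|---|---|
| 80%/60% | .067 | .1136, .1133 | 9.0% | 9.3% | 5.4% |
| 80%/50% | .106 | .1140, .1130 | 15.1% | 15.8% | 13.3% |

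With no response bias and the same responder numbers, Fisher's test rejects in only 2.6% (36 v 36) and 3.5% (34 v 36). The 5.4% therefore reflects Fisher's conservatism absorbing the bias; the 6.7-point error in the estimate is the same under either test.

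**5. Precision.** With the formula in step 1 and .74 as the reference, the difference detectable with 80% power is .271 at 50 responders per arm, .304 at 40 and .325 at 35. This shows only how quickly information is lost; it does not correct a survey power claim, because the plan makes none.

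**6. Are the items the same?** Section 2 and section 5 (Study Instruments) say that the follow-up repeats the baseline questions on knowledge, attitudes and willingness. Section 3 says that only some of them are repeated. Section 10 allows skipping, so a completed baseline survey need not contain every item.

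**The case against.** The strongest objection is that analysis sets, missing answers and baseline adjustment are usual content of a statistical analysis plan, which is not at hand. A reader might infer that the protocol prescribes a responders-only analysis and so abandons the randomised comparison. The text does not say that: section 2 names tests and is silent on the analysis set. That part of the objection stands. What remains is that the method actually named uses neither the baseline answer nor the stratum, and that how the phone call is used is a data-collection matter. An analysis plan cannot recover answers that were never taken.

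Second, the sentence on reminders is itself a safeguard. With up to three e-mails, a call, a separate gift certificate and a one-week interval, response may be high. This stands, and it lowers the likely size of the problem. Nothing in section 3 forbids taking answers by phone; it simply does not provide for it.

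Third, the size is wholly assumed. The scenarios that produce bias let response depend on willingness in one arm only. With the same dependence in both arms the false difference is zero, and under Fisher's test the milder scenario is close to nominal. This stands too, and is why the range begins at zero.

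Fourth, a reader might infer that the main result or the stated .28 is weakened. Neither is. Both primary objectives rest on the provider's form and medical records, and the .28 concerns asking the provider.

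**Conclusion.** The point holds for the survey outcomes only. The sole measure of willingness, knowledge and barriers after education is remote and open to non-response, and the named unadjusted test leaves unused the baseline answers and the stratum that the design already supplies.

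Under the assumed rates (60% true willingness in both arms, 68 to 72% response), the false difference runs from 0 to about 11 points. The scenarios with unequal dependence give about 7 and 11 points, with false positives of about 9 and 16% by Pearson or 5 and 13% by Fisher. Bias in the arm difference at no true effect requires response to depend on willingness differently by arm. The design makes that plausible; the documents do not show that it will happen. It is a worthwhile, inexpensive improvement and no threat to the primary analysis.

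**What to change.** 1. **Section 3.** State that participants reached by the planned call may answer the core willingness, knowledge and barrier items on it, and record the mode of completion. Cost: a short script on a call already planned. Downside: a possible mode effect on sensitive items, which the recorded mode allows to be examined.

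2. **Section 2.** Compare these outcomes by assigned arm with a logistic model that includes the baseline answer to the same item and the MSM stratum, covering all randomised participants, for example by multiple imputation or a two-time-point mixed model. Keep the unadjusted responders-only test as a sensitivity analysis, and report response by arm. Cost: modest programming in SAS, which the plan already uses. Limit: the model removes bias only so far as baseline answer, arm and stratum explain who replies, which is why the first change matters as well.

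3. **Sections 2, 3 and 5.** Confirm that the core items appear in both surveys and make the three descriptions agree. The adjustment depends on it.

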#### 4. STUDY DRUGS AND DEVICES

Not Applicable

#### 5. STUDY INSTRUMENTS

We will be distributing an initial questionnaire (either in electronic or hard-copy format) to collect data on:

1. Patients' demographic information, sexual behavior and health, and drug use
2. Patients' baseline knowledge, attitudes, and willingness to use oral PrEP
3. Patient's acceptance of other methods of prevention HIV methods

The second questionnaire (e-mailed to the patients using SurveyGizmo) will ask the same questions in 2 and 3 as above.

Questionnaires attached:

1. Initial Survey to Assess Knowledge, Attitudes, and Willingness to Use PrEP Among High-Risk Adolescents and Young Adults.doc
2. Follow-up Survey to Assess Knowledge, Attitudes, and Willingness to Use PrEP Among High-Risk Adolescents and Young Adults.doc

#### 6. STUDY SUBJECTS

We plan to study HIV-negative, young adults age 18-25 who see providers at Project Stay, a Columbia-affiliated clinic catered to adolescents at high-risk for acquiring HIV infection.

#### 7. RECRUITMENT

We will work with Project Stay to figure out the best way to approach and talk to patients about the study, which will likely be when they are waiting to be seen by their providers.

#### 8. INFORMED CONSENT PROCESS

After reading about the purpose of our study, informed consent will be obtained using a hard-copy that must be signed before participation in the study. Participants will be provided with a copy of the informed consent and may withdraw from the study at any time.

#### 9. CONFIDENTIALITY OF STUDY DATA

Study data will be collected both via hard-copy materials and electronically, using participant ID numbers. In addition, their MRN will be used to obtain information on provider prescribed PrEP medications and filled PrEP prescriptions. The records of this study will be kept in a secure fashion. In any sort of report we make public we will not include any information that will make it possible to identify participants and data will be reported in aggregate. Research records will be kept in a password-protected file and locked cabinet; only the investigators will have access to the records.

#### 10. PRIVACY PROTECTIONS

Only those conducting the study will have access to participants' information. Furthermore, participants may choose to not answer any question in the questionnaire if it makes them feel uncomfortable or skip a question for any reason.

#### 11. POTENTIAL RISKS

We do not foresee any potential risks associated with participating in our study other than providing potentially sensitive information about their social history. However, this is no different from what may be asked in obtaining a normal patient history.

#### 12. DATA AND SAFETY MONITORING

Not applicable

#### 13. POTENTIAL BENEFITS

Personal benefits for participants to partake in our study may include increased knowledge of a potentially effective HIV prevention method. In addition, information gained as a result of this research may advance knowledge in this area and help others in the future, including informing educational interventions on PrEP use and the direction of future research in the use of PrEP for the prevention of HIV. It may also aid in the development of educational materials geared toward increasing awareness among high-risk adolescents and adults on risks and concerns of using antiretrovirals for prevention of HIV.

#### 14. ALTERNATIVES

The study participants can choose not to participate.

#### 15. RESEARCH AT EXTERNAL SITES

Not Applicable

#### 16. COLUMBIA AS LEAD INSTITUTION

Not Applicable

